5.5 Study Evaluations

Screening and Consenting Visits:

This visit will last approximately 60 minutes in duration and will occur in the morning at the Endocrinology Clinic space at the VA Hospital. Subjects will be asked to come after an overnight fast before their arrival at the clinic. Subjects will be asked to avoid tobacco use on the morning of scheduled visits. Informed written consent will be obtained by [name] in a private environment. The decision to participate or not will not influence medical care by the co-PI or any other member of the team. After informed consent has been obtained, the following procedures will take place: 1) anthropometric measurements (waist circumference, height, body weight); 2) seated blood pressure measurements (in triplicate) after five minutes of rest, heart rate, temperature, and respirations 3) resting 12-lead ECG; 4) phlebotomy to obtain blood sample for serum chemistries, HbA1c, lipid panel, thyroid, liver, kidney function, hemoglobin and hematocrit and coagulation tests (prothrombin time, and activated partial prothrombin time). Once screening tests have been completed and resulted, enrollment eligibility will be reviewed by co-PIs, [name] and [name].

Eligibility:

Eligible subjects will be scheduled for four outpatient study visits (2 equipment fitting visits-1 hour duration each, and pre- and post-treatment assessment, eight hours duration each) at the Clinical Translation Science Unit (CTSU) of the University of Missouri, a core facility and one outpatient study visit at the Harry S. Truman VA Hospital (safety labs). The first study visit will be scheduled within four weeks of the screening visit. Participants will be instructed to maintain their habitual physical activity levels and dietary habits throughout the eight-week period. Adherence to the supplement/placebo will be facilitated (and documented) by the following processes: 1) the study coordinator/research nurse will review proper adherence directions at baseline visit; 2) capsule boxes will be provided at the baseline visit and the participant will be asked to bring the box at the post-treatment visit to count any remaining capsules; and 3) participants will be contacted on a weekly basis by the study coordinator to check in and review compliance.

Equipment fitting visits and potential risks:

In the week leading up to the pre and post assessment visits, the subjects will attend an appointment with the purpose of being fitted with an ambulatory blood pressure monitor. The subjects will be instructed on the wear and use of the ambulatory blood pressure system and will take the equipment with them for home use over a 24-hour period. Subjects will also be instructed on the use of the Glycocheck equipment and practice collecting measurements.

Ambulatory blood pressure monitoring: Blood pressure monitoring will be conducted with a Welch Allyn ABPM 7100 Ambulatory Blood Pressure Monitor or equivalent device and adult blood pressure cuff. This procedure is not standard of care. This procedure poses no risks but may cause some discomfort due to cuff inflation.

Assessment visits and potential risks:

At each CTSU visit, subjects will arrive after an overnight fast, having not taken medications the morning of the study, and not exercised for 24 hours. Subjects will be asked to avoid tobacco use on the morning of scheduled visits. Anthropometric (waist circumference, height and body weight), body composition (via DEXA) and blood pressure measurements will be obtained. At this time, a three-day dietary recall will be performed by a registered dietitian at the CTSU and analyzed using NDSR software. Subsequently, subjects will be placed supine in a quiet, climate-controlled room (22–23°C) for measurements to be performed are described below.

Time point	Blood volume (mL)
Screening	20
Baseline visit	70
Safety visit	10
Final Visit	80
Total	180
*Unscheduled safety labs (10)	

Box 1. Expected blood draw volumes during the duration of the study.

Phlebotomy: The total blood withdrawn will not exceed 180 mL throughout the study period (**Box 1**). Hematocrit and Hemoglobin (H&H) is measured during screening, safety labs, and at final visits to check that it is within safe limits. All subjects will be advised to refrain from donating blood during public blood drives, during their participation in this project. These activities are associated with a small risk of phlebitis, bruising, fainting and minor pain. Antiseptic technique will be used by nurses who are experts in phlebotomy and catheter placement. If phlebitis occurs, it will be treated conservatively with heat and when appropriate, with antibiotics. The risk of bleeding is reduced by applying pressure at the site of puncture. Bruising is treated with ice. Fainting is prevented by drawing blood in the semi-recumbent position.

Safety Labs: Subjects will have safety labs drawn at 7-14 days after beginning study medication. Safety labs will be drawn at the Harry S. Truman VA Hospital. In case of abnormal results in laboratory values obtained during the study, the safety office will determine the clinical significance of those findings and the appropriate course of action.

Additional Safety Visits/unscheduled visits: Additional safety labs/visits can be scheduled at the discretion of the study's safety officer. Amount of blood draw for safety labs will not to exceed 10mL. Unscheduled visits may also occur if safety lab specimens are compromised for any reason or questionable accuracy of the result. Safety labs will then be repeated (amount of blood drawn not to exceed 10 mL).

Glycocheck: The Glycocheck video microscope instrument will be placed under the subject's tongue to measure capillaries, blood vessel density, red blood cell concentration, flow rate, and red blood cell penetration of the glycocalyx lining. Glycocheck is an FDA Class 1 Medical Device. This procedure is not standard of care. This procedure poses no risks.

Pulse wave velocity: A special non-invasive device will be used to assess blood pressure and flow. A blood pressure cuff will be wrapped around the upper arm and upper leg of the participant. The cuffs will periodically inflate to squeeze tightly for less than 60 seconds. A pressure sensor, the size of a pencil will be placed over the skin of the neck region to obtain the pressure wave form in the neck vessel (i.e., carotid artery). This procedure takes about 15 minutes. Risks: The blood pressure cuff will squeeze the arm and leg tightly; however, any discomfort will be alleviated as soon as the pressure in the cuff is released. This procedure is not standard of care.

Brachial and femoral artery FMD: Arterial measurements will be performed by imaging the brachial or femoral artery longitudinally using high-resolution duplex ultrasonography. Arterial vasodilatory responses to hyperemia (i.e., FMD) will be examined by inflating a forearm or leg cuff up to 250 mmHg for five minutes. Before, during and after rapid release of the cuff, brachial artery blood flow velocity and diameter will be continuously measured. When assessing FMD, the blood pressure cuff will squeeze the arm or leg tightly; however, any discomfort will be alleviated as soon as the pressure in the cuff is released. This procedure is not standard of care.

Insulin and Glucose infusion: A 1-hour insulin and glucose infusion, coupled with measurements of leg blood flow, will be performed following standard procedures at the University Hospital CTSU. Subjects will be instrumented for measures of heart rate (using standard lead II ECG), arterial blood pressure (using automated sphygmomanometry and/or beat-to-beat blood pressure via Finometer), and leg blood flow (using duplex Doppler ultrasound and contrast-enhanced ultrasound, CEU). After a minimum of 20 minutes supine rest, baseline cardiovascular measurements will be collected, blood samples obtained and the insulin infusion will start. Insulin diluted in 0.9% saline with 5 mL of the subject's blood is infused at a constant infusion of $80 \text{ mU} \cdot \text{m}^{-2} \cdot \text{min}^{-1}$. Glucose is maintained at fasting values throughout via a variable 20% dextrose infusion. Leg blood flow, arterial blood pressure, and heart rate will be collected for 5-minute periods at 15-minute intervals throughout a 60-minute insulin infusion allowing the magnitude as well as the temporal profile of these variables to be determined. For microvascular blood flow using CEU, measurements will be performed before and during the first 60 minutes of insulin infusion. Briefly, assessment of microvascular perfusion utilizing CEU involves

ultrasound imaging of the leg skeletal muscle during the administration of one vial (1.3 mL) of an ultrasound contrast agent diluted in 30 mL of 0.9% saline that will be given using a handheld syringe pump through the IV at a rate of 2 mL/min. This agent, called Definity, is composed of tiny microbubbles smaller than the size of a red blood cell. These bubbles stay inside the blood vessels and go where the red blood cells go. This contrast agent allows us to evaluate microvascular blood flow. Definity has been FDA approved for use in humans during ultrasound of the heart cavity and has been shown to be safe. The total volume of blood drawn per insulin infusion is approximately 52mL. The potential risks during this procedure include mild nausea or light-headedness, and mild to moderately high or low blood glucose levels. However, blood glucose will be continually monitored during the infusion of insulin and dextrose will be available if needed to counteract hypoglycemia. Also, drinks and snacks will be available for the subjects at the completion of testing should they have low blood sugar or feel nauseous. Subjects are monitored for a minimum of one hour post insulin infusion. This procedure is routinely performed by Drs. [name] and [name]. [name], board-certified endocrinologist, will be available during the procedures. This procedure is not standard of care.

Skeletal muscle perfusion assessment using Perflutren (Definity): A potential side effect from the Perflutren ultrasound contrast agents is temporary back pain, joint pain, headache, shortness of breath, or flushing. These symptoms occur in about one in 200 subjects and are mild in intensity in 90% of those who experience this reaction. If this happens infusion of the agent will be stopped. The back and joint pain will go away in a few minutes. A serious allergic reaction to ultrasound contrast agents is unlikely (1 in 10,000), but possible. Symptoms of an allergic reaction include: Rash, itching, swelling, severe dizziness, chest pain and trouble breathing. We are using this contrast agent to measure microvascular perfusion in skeletal muscle using a dose approved by the FDA. This procedure is not standard of care.

DEXA and anthropometrics: Radiation exposure during DEXA is equivalent to about 2% of the average radiation dose from all sources (natural background radiation, consumer appliances, radon gas, medical tests, etc.) that a person in the United States receives each year. Subjects who participated in any other research study or medical procedure involving significant ionizing radiation exposure (e.g., multiple chest x-rays) in the past 12 months will be excluded. Only postmenopausal subjects will be included in the study; therefore no pregnancy test will be pursued. Body weight is measured to the nearest 0.1 kg and height to the nearest 0.1 cm. This procedure is not standard of care.

Dietary Recall/Assessment: The study dietitian or a trained research technician will interview research subjects about the foods and beverages that they have recently consumed or asked them to keep a record of the foods that you consume for 3 days. There are no risks with this procedure. Dietary Recall/Assessment will be performed at the preassessment and post assessment visits.

Supplement, Endocalyx: The Dietary Supplementation of Glycocalyx Precursors (DSGP) commercially available as Endocalyx™ (Microvascular Health Solutions LLC, Alpine, UT) which includes: glucosamine sulfate, fucoidan, superoxide dismutase, and high molecular weight hyaluronan is the supplement being compared to placebo in this study. In addition, we will monitor coagulation tests (PT and PTT) at baseline, 7-14 days (this blood check will occur at VA main hospital) and during final visit. There are no known risks associated with supplementation with DSGP. Nevertheless, subjects with known allergies to any of the compounds in the supplement (glucosamine extract, fucoidan extract, olive extract, artichoke extract, red and white grapes extract, melon concentrate, hyaluronic acid) will not be included in the study. If subjects exhibit changes in their health status across any system related or unrelated to the study intervention, [name] (safety officer) will be consulted for advice. Study subjects will be responsible for taking the study supplement or placebo at home, daily for the span of 2 months. The study team will monitor dosing compliance weekly. The use of Endocalyx in this study is filed under the research IND 164629 that was submitted on 11/23/2022.

Randomization and Blinding: Subjects will either take a placebo or a supplement as part of this study. There is an equal but random chance that a subject will be assigned to either the placebo or

supplement treatment. The study team will be blinded to the study treatment. There is no risk associated with randomization or blinding in this study.

Heart rate measurements via ECG: Heart rate will be measured. Some people may have a skin irritation from the patches that connect the wires on your chest to the computer. Skin and hair are pulled slightly when the patches are removed after the test. Research personnel will attach and remove the patches as carefully as possible. Heart rate monitoring will occur at screening, preassessment, and post assessment visits.

Insertion of venous catheters: IVs will be placed to collect blood during study assessments. The potential risks of venous catheterization include infection, swelling and discomfort at the catheter insertion sites. Some bleeding may occur during the insertion of the catheters as well after the catheters have been removed. There is also the possibility of fainting, dizziness, and possible pain and bruising as a result of catheter insertion. These risks will be greatly minimized by using sterile procedures and having an experienced registered nurse placing the venous catheters. Insertion of IVs will occur at preassessment and post assessment.

Medication hold the morning of the study visits: Subjects will be instructed to hold diabetes medications the morning of the CTSU visit to minimize the risk of hypoglycemia. These medications include: insulin, sulfonylureas, gliptins, metformin, acarbose, GLP-1 analogs, inhibitors of the sodium glucose co-transporters. [name] will review medications ahead of the visit and instruct subject which medications to hold.

Transport via wheelchair: If research procedures are completed in both CTSU locations during the same visit, participants will be transported via wheelchair between locations. Wheelchair transport will minimize the physical strain on research participants as well as reduce the vascular impact of ambulating during a study visit. Study staff assisting in wheelchair transportation will be trained on common safety practices to minimize risk of injury and/or fall to the participants and themselves.

5.6 Data Analysis

For Aim 1 of the study, twenty-four subjects (**n=24**) will be enrolled in the DSGP/placebo treatment with 12 subjects randomized to each group. For Aim 2 of the study, seventy-two subjects (**n=72**) will be enrolled with eighteen subjects randomized to each of the four interventions.

Statistical analysis, sample size and power calculations:

Aim 1: We will analyze change in PBR (and change in other secondary outcomes) using ANCOVA with baseline PBR as a covariate and dietary supplement as a main effect. We will use residual diagnostic plots to check for violations of assumptions on normality and equal variance among groups. If variance is not equal, separate variance components can be estimated in SAS mixed procedure to account for these differences. Inspection of the variance estimates and a likelihood ratio test can validate the need for this approach. Transformation may be used to correct for skewness and unequal variance. This analysis has two treatment levels to contrast and no need for multiple contrast correction like Bonferroni.

Power estimates are based on preliminary data in PBR (for Aim 1) and FMD (for Aim 2). We observed a mean of 1.742 (standard deviation, SD=0.27) and 1.45 (SD=0.20) in PBR for type 2 diabetes (T2D) and healthy subjects, respectively. Based on our findings in the pre-clinical mouse model of T2D that glycocalyx thickness was completely restored with DSGP, we predict that DSGP in T2D subjects will cause a mean decrease in PBR of 0.3, with no changes in response to placebo. As presented in Figure 3E, we observed a mean of 3.78 (SD=1.86) and 7.06 (SD=2.21) in FMD for T2D and healthy subjects, respectively. We predict that DSGP + exercise will cause a mean increase in FMD of 2, which represents two-thirds of the distance between healthy and T2D subjects. Our pilot data was also

used to estimate the within-subject variance, assuming a correlation of $r=0.6$ between serial measurements on the same subject.

For Aim 1, assuming pre-treatment PBR $SD=0.27$, post $SD=0.20$, and correlation between pre and post is 0.6 , then the SD of the pre to post treatment change in PBR is 0.22 . A sample size of $n=10$ per group will provide 82% power when the true mean difference in PBR change is 0.3 . Adjustment of sample size for 20% attrition results in 24 subjects (12 per group) for Aim 1 and 72 subjects (18 per group) for Aim 2.

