3.0 Objectives

Our overarching hypothesis is that endothelial glycocalyx degradation is a key factor that precludes shear stress mechanotransduction and consequent exercise-induced vascular adaptations in T2D. (Figure 1). A corollary to this hypothesis is that restoration of the endothelial glycocalyx by DSGP will improve vascular adaptations to exercise in T2D.

Specific aims are as follows:

Aim 1 (Proof of Concept Clinical Trial Phase): Document that DSGP enhances endothelial glycocalyx integrity in Veterans with T2D. Although we provide preliminary evidence that DSGP can increase glycocalyx thickness and endothelial function in a mouse model of T2D, this will be the first study to demonstrate these effects in T2D subjects. The effects of DSGP for eight weeks on glycocalyx integrity and endothelial function will be studied using a double-blinded randomized placebo control trial.

Aim 2 (Expanded Clinical Trial Phase): Demonstrate the permissive role of the endothelial glycocalyx for exercise-induced vascular adaptations in Veterans with T2D. Having shown that endothelial glycocalyx restoration via DSGP in T2D subjects is feasible, we will now investigate whether such supplementation potentiates exercise training-induced improvements in endothelial function. This will be accomplished with a factorial balanced design in which T2D subjects will be randomized to DSGP or placebo with and without concurrent exercise training for eight weeks.

RELEVANCE TO VETERANS AND THE VA: Targeting the glycocalyx holds extraordinary promise for achieving optimal exercise-induced vascular adaptations in T2D, thus maximizing the cardiovascular benefits of exercise.

[figure not shown]

Figure 1. Overarching hypothesis: Endothelial glycocalyx degradation (left side) is a key factor precluding shear stress mechanotransduction (i.e., it renders the endothelium unable to detect shear stress forces) that makes T2D individuals exhibit diminished exercise-induced vascular adaptations. Restoration of the glycocalyx (right side) reinstates shear stress echanotransduction, permitting optimal exercise-induced vascular adaptations.

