5.0 Study Procedures (*Proof of Concept Clinical Trial Phase*)

5.1 Study Design

Aim 1 (*Proof of Concept Clinical Trial Phase*): Document that DSGP enhances endothelial glycocalyx integrity in Veterans with T2D.

Rationale. Based on our preliminary data showing that DSGP augments endothelial glycocalyx thickness and vasodilatory responses in a mouse model of T2D (**Figure 2**), the purpose of this Aim is to demonstrate that these effects are applicable to Veterans with T2D. Importantly, our results should establish for the first time that glycocalyx restoration is accompanied by improvements in endothelial function, providing support for our proposal that the glycocalyx is a key therapeutic target to combat vascular complications in diabetes. Finally, the results obtained in Aim 1 will set the stage for an expansion of the clinical trial (Aim 2) designed to elucidate if restoration of the endothelial glycocalyx enhances exercise training-induced vascular adaptations in T2D subjects.

Hypothesis. We hypothesize that DSGP will enhance endothelial glycocalyx integrity in T2D subjects and that this effect will be associated with increased shear stress mechanotransduction and endothelial function.

Study Design and Recruitment of Participants. We will employ a double-blinded randomized placebo control trial designed to determine the effects of DSGP on endothelial glycocalyx integrity and endothelial function

(**Figure 9**). Veterans diagnosed with T2D (n=24), 45- 74years of age, will be recruited from the Harry S. Truman Memorial VA Hospital in Columbia, Missouri. The selected age range aligns with data from the Centers for Disease Control, indicating that the incidence of T2D in Veterans continues to increase after even after 65 years of age.⁴ Subjects will be classified as having T2D based on physician diagnosis, following the American Diabetes Association guidelines.⁵¹

Randomization and Blinding. Participants will be assigned to DSGP or placebo using block randomization to achieve balance in the allocation of participants to treatment arms. Randomization order will be provided to the investigational pharmacy for intervention allocation. Preparation and administration of the supplement/placebo capsules will be directed by the VA Hospital Investigational Pharmacy. All members of the investigative team involved in data acquisition and analysis will be blinded to group assignment, and subjects will not be informed of their group status.

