5.4 Inclusion/Exclusion Criteria

Inclusion:

- 1) 45-74 years of age at the time of enrollment
- 2) Diagnosis of T2D by a health care provider, confirmed by chart review
- 3) HbA1c <9% and fasting blood glucose <200 mg/dL at screening visit
- 4) Body mass index (BMI) 25–45 kg/m²
- 5) Women should be postmenopausal (absence of menses for at least 1 year)
- 6) Sedentary subjects (<2 days/week of vigorous exercise)
- 7) Willingness to follow up instructions provided by study team

Exclusion:

- 1) Evidence of cardiac arrhythmias, unstable angina (or other cardiac event), heart failure or stroke in the last 12 months
- 2) Evidence of chronic kidney disease stage IV or V (GFR <30 mL/min)
- 3) Evidence of uncontrolled hypertension, systolic blood pressure > 180 mmHg and/or diastolic blood pressure > 110 mmHg on more than 2 occasions in the past 12 months or at screening visit
- 4) Diagnosis of chronic liver disease
- 5) Uncontrolled thyroid dysfunction (abnormal TSH within 3 months of study enrollment)
- 6) Active cancer
- 7) Current use of hormone replacement therapy
- 8) Excessive alcohol consumption (>14 drinks/week for men, >7 drinks/week for women)
- 9) Current pregnancy or intent to become pregnant during the course of the study
- 10) Inability to swallow capsules
- 11) Known allergies to any of the compounds in the supplement: glucosamine extract, fucoidan extract, olive extract, artichoke extract, red and white grapes extract, melon concentrate, hyaluronic acid

	Screening Visit	AMBP Fitting (Day -7 to -2)	Pre- Assessment (Day 0)	Safety Blood Draw (Days 7-14)	Dosing Window (Days 1-56)	AMBP Fitting (Day 49-54)	Post- Assessment (Day 56)
Informed consent form signing	X						
Medical history	X						
Concomitant medication assessment	X		X		X	X	X
Height assessment	X		X				X
Weight assessment	X		X				X
Waist circumference assessment	X		X				X
Vitals signs (blood pressure, heart rate and respiratory rate, temperature)	X		X				X
12-lead ECG	X						
Fasted bloodwork: HbA1c, FLP, CMP, TSH, H&H	X						
Bloodwork: PT, PTT, H&H	X			X			X
3- Day food diary		X				X	
24-hour Ambulatory Blood Pressure Monitoring (AMBP)		X				X	
24-hour AMBP activity log		X				X	
AM T2D medication hold			X				X
AM Tobacco hold	X		X				X
24-hour exercise hold	X		X				X
Overnight fasting	X		X				X
Fasted blood draw			X				X
Glycocheck		X	X				X
Pulse Wave Velocity			X				X
Brachial FMD			X				X
Femoral FMD			X				X

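### Read literally, the Aim 1 ANCOVA adjusts change in secondary outcomes such as FMD for baseline PBR rather than for their own baseline, which costs precision; one sentence would settle it.

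*Combined protocol and SAP*

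**What the plan says.** The Aim 1 paragraph of section 5.6 gives one model for all outcomes: "change in PBR (and change in other secondary outcomes) using ANCOVA with baseline PBR as a covariate and dietary supplement as a main effect". It adds checks on residuals and variances, and closes with "This analysis has two treatment levels to contrast and no need for multiple contrast correction like Bonferroni". No other analysis of the secondary outcomes appears in the visible text, and nothing there says that each outcome is adjusted for its own baseline.

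The visible text does not list the Aim 1 secondary outcomes, but endothelial function is plainly an Aim 1 question. Section 3.0 states "The effects of DSGP for eight weeks on glycocalyx integrity and endothelial function will be studied", and section 5.1 describes a trial "designed to determine the effects of DSGP on endothelial glycocalyx integrity and endothelial function". Table 1 (section 5.4) schedules brachial and femoral FMD at Day 0 and Day 56. Pulse wave velocity, contrast-enhanced ultrasound and the insulin-infusion measurements fall on the same two days. Ambulatory blood pressure is recorded on Day -7 to -2 and again on Day 49-54. FMD is therefore well supported as a secondary outcome; the others are inferred from the schedule.

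**The concern.** The gain from ANCOVA on a change score comes from a covariate that predicts the outcome. For change in FMD the obvious candidate is baseline FMD. It removes regression to the mean and corrects for chance imbalance between arms. Baseline PBR does so only to the extent that it is correlated with FMD. If that correlation is weak, the analysis as written is close to an unadjusted comparison of change scores and also spends a degree of freedom on the covariate.

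With 10 to 12 participants per arm, chance imbalance in baseline FMD can be sizeable, and part of it would stay in the estimate. The sentence can also be read in two ways, so two analysts could follow it and report different FMD results. That choice should not be left until the data are in hand.

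**Working it through.** **The plan's own figure.** Section 5.6 assumes a pre-treatment PBR SD of 0.27, a post-treatment SD of 0.20 and a correlation of 0.6. The SD of change is √(0.27² + 0.20² − 2 × 0.6 × 0.27 × 0.20) = √0.0481 = 0.219, which agrees with the stated 0.22. With 10 per arm and a difference of 0.3, a two-sided t-test at 0.05 (the level is not stated and is assumed here) has 82.2% power. The stated 82% reproduces, and this concern does not affect it.

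**Inputs for FMD.** Section 5.6 reports "we observed a mean of 3.78 (SD=1.86) and 7.06 (SD=2.21) in FMD for T2D and healthy subjects, respectively" and a serial correlation r of 0.6. Take s₀ = 1.86 before treatment and n = 10 evaluable per arm. No post-treatment FMD SD is given for Aim 1, so two values of s₁ are shown: 2.21 (the healthy-subject SD) and 1.86 (no change).

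**Residual variance of FMD change.**
- As written, with baseline PBR unrelated to FMD: s₀² + s₁² − 2·r·s₀·s₁
- With baseline FMD as covariate: s₁²·(1 − r²)

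| Post SD | As written | Own baseline | Variance ratio | CI width ratio |
|---|---|---|---|---|
| 2.21 | 3.411 | 3.126 | 1.09 | 1.045 |
| 1.86 | 2.768 | 2.214 | 1.25 | 1.12 |

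Both models have one covariate and 17 residual degrees of freedom, so the comparison is like for like.

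**Sensitivity to r.** For r from 0.4 to 0.8 the variance penalty runs from 23% down to 0.5% (post SD 2.21), or from 43% down to 11% (post SD 1.86).

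**Sensitivity to the link between PBR and FMD.** The documents give no figure for this link.
- *Link through baseline FMD only.* If baseline PBR correlates −0.3 to −0.5 with baseline FMD, the penalty is 8% to 7% (post SD 2.21) or 23% to 19% (post SD 1.86).
- *Direct link to FMD change.* If baseline PBR correlates ρ with FMD change, the as-written variance is multiplied by (1 − ρ²). With post SD 1.86 the penalty is 20% at ρ = 0.2 and 5% at ρ = 0.4, and it is gone at ρ = 0.45. With post SD 2.21 it is 5% at ρ = 0.2 and gone at ρ = 0.29. At these thresholds baseline PBR predicts FMD change as well as baseline FMD does; beyond them it would be the better covariate.

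**Chance imbalance.** The standard error of the baseline FMD difference is 1.86 × √(2/10) = 0.83 points. The slope of change on own baseline is r·s₁/s₀ − 1, which is −0.287 (post SD 2.21) or −0.40 (post SD 1.86). A one-SE imbalance therefore moves the as-written estimate by 0.83 × 0.287 = 0.24 or 0.83 × 0.40 = 0.33 points. With the PBR–FMD correlations of −0.3 to −0.5 above, the shift is 0.18 to 0.30 points.

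**Simulation (40,000 trials, 10 per arm).** The documents give no Aim 1 effect on FMD, so the Aim 2 difference of 2 points is used for illustration only.

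| Post SD | Power as written | Power, own baseline |
|---|---|---|
| 2.21 | 60% | 64% |
| 1.86 | 69% | 79% |

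Type I error as written was 5.1% and 4.9% respectively. A separate simulation of 20,000 trials per setting gave matching power and showed both models to be unbiased.

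**The case against.** The strongest reply is that the sentence is shorthand. PBR is the worked case throughout the paragraph, the secondary outcomes sit in a parenthesis, and many readers would take it to mean each outcome with its own baseline. That may well be the intent. It does not remove the point, because the literal text says otherwise and nothing visible corrects it.

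The second reply concerns size. For PBR the plan pairs the T2D SD before treatment with the healthy-subject SD after. The same convention for FMD gives 1.86 and 2.21, which leads to the 9% figure; the 25% needs an assumed equal SD. This is fair, and 9% is the case closer to the plan's own pattern.

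Third, the trial's hypothesis makes a direct relation between baseline glycocalyx state and FMD response plausible, and such a relation could shrink or remove the penalty. This stands as a limit on the estimate, although the documents give no data for it.

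Fourth, the 2-point difference is predicted for DSGP plus exercise, and Aim 1 has no exercise. The power figures therefore show scale only and are not a forecast for Aim 1.

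Finally, an outcome list may have stood in the Aim 1 design figure, which is not shown. The statement that secondary outcomes are not listed applies to the visible text.

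**Conclusion.** The concern holds. As written, change in FMD and other secondary outcomes is adjusted for baseline PBR, and this is less precise than own-baseline adjustment under the stated assumptions. The variance penalty for FMD is about 9% (post SD 2.21) to 25% (post SD 1.86) at r = 0.6 with baseline PBR unrelated to FMD. It could approach zero if baseline PBR strongly predicted FMD change. Validity is not at issue, and the primary PBR analysis and the sample size are unaffected. The loss is modest, but it falls on an endothelial-function question that Aim 1 sets out to answer, and avoiding it costs nothing. It should be fixed before analysis.

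**What to change.** Replace the Aim 1 model sentence in section 5.6 with wording such as:

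> Change in each outcome will be analysed by ANCOVA, with treatment group as the factor and that same outcome's pre-treatment value as the covariate.

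Then name the baseline wherever it is not obvious, for whichever of these measures are outcomes:
- PBR: baseline PBR.
- Brachial or femoral FMD: the Day 0 value at the same site.
- Ambulatory blood pressure: the Day -7 to -2 recording.
- Leg blood flow and contrast-enhanced ultrasound: the Day 0 visit value of the same derived measure. If the outcome is the insulin-stimulated change, the covariate is the Day 0 insulin-stimulated change.

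If this was already the intent, the edit is a clarification. The cost is one sentence in section 5.6, because the pre-treatment values are already scheduled. No new data, visits or patients are needed.
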